PROTOCOL TITLE	A phase 2 open-label study to assess the safety and immunogenicity of an alum-adjuvanted chikungunya virus-like particle vaccine (PXVX0317) in prior recipients of other alphavirus vaccines versus alphavirus naïve controls
SITES	Two US sites, Walter Reed Army Institute of Research (WRAIR) Clinical Trials Center (CTC) and US Army Medical Research Institute for Infectious Disease (USAMRIID) immunization clinic.
OBJECTIVES	
It is currently unknown whether prior exposure to heterologous alphaviruses will enhance or interfere with immune responses to chikungunya virus (CHIKV) exposure or vaccination. The objective of this study is to evaluate the safety and immunogenicity of the chikungunya vaccine candidate PXVX0317 when administered to prior recipients of experimental alphavirus vaccines versus alphavirus naïve gender and age-matched controls.
 
Safety Objectives
 
 • Evaluate the safety of PXVX0317 when administered to prior alphavirus vaccine recipients versus gender and age-matched controls. 
Immunogenicity Objectives
 
Primary
 
 ▪ Evaluate the neutralizing antibody response to chikungunya virus induced by PXVX0317 when administered to prior alphavirus vaccine recipients versus gender- and age-matched controls. 
Secondary
 
 ▪ Evaluate the overall antibody responses to CHIKV and Venezuelan equine encephalitis virus (VEEV) induced by vaccination with PXVX0317 when administered to prior alphavirus vaccine recipients versus gender and age-matched controls. 
Exploratory
 
 ▪ Evaluate the cellular immune response to chikungunya virus induced by vaccination with PXVX0317 when administered

	
to prior alphavirus vaccine recipients versus gender and age-matched controls.
 
 ▪ Evaluate the humoral immune responses to eastern equine encephalitis virus (EEEV) and western equine encephalitis virus (WEEV) induced by vaccination with PXVX0317 in selected subjects who previously received these vaccines versus alphavirus-naïve controls. ▪ Collect human immunoglobulin for use in a mouse challenge study. ▪ Evaluate the ability of CHIKV antibodies to PXVX0317 to neutralize diverse alphavirus strains.
PRIMARY IMMUNOGENICITY ENDPOINT	
The anti-CHIKV seroconversion rate at Day 22 in prior alphavirus vaccine recipients versus alphavirus-naïve controls, where seroconversion is defined as a 4-fold rise over baseline in anti-CHIKV neutralizing antibodies as determined by a luciferase-based assay (NT₈₀).

SECONDARY AND SAFETY ENDPOINTS	
Secondary Immunogenicity Endpoints
 
 • Anti-CHIKV neutralizing antibodies, determined by luciferase-based assay (NT₈₀), in prior alphavirus vaccine recipients versus alphavirus-naïve controls, assessed by 
 - Geometric mean titer (GMT) and geometric mean ratio (GMR) on Days 1, 8, 22, 29, 57 and 182 - Seroconversion rates on Days 8, 29, 57 and 182 - The proportion of subjects with titers of at least 40, 160 or 640 on Days 1, 8, 22, 29, 57 and 182 • Anti-CHIKV total antibodies, determined by immunoassay, in prior alphavirus vaccine recipients versus alphavirus-naïve controls, assessed by 
 - GMT and GMR on Days 1, 22 and 29 - Seroconversion rate on Days 22 and 29 where seroconversion is a 4-fold rise in titer over baseline - The proportion of subjects with titers of at least 40, 160 or 640 on Days 1, 22 and 29 • Anti-VEEV total and neutralizing antibody, as determined by immunoassay and Plaque-Reduction Neutralization Test (PRNT₈₀) respectively, in prior alphavirus vaccine recipients versus alphavirus-naïve controls, assessed by

	
 - GMT and GMR on Days 1, 22 and 29 - Seroconversion rate on Days 22 and 29 where seroconversion is a 4-fold rise in titer over baseline - The proportion of subjects with titers of at least 40, 160 or 640 at Days 1, 22 and 29 
Safety Endpoints
 
The safety and tolerability endpoints include local and systemic post-injection solicited events and other adverse events collected during the 7 days following the injection. Safety endpoints also include the occurrence of any unsolicited adverse events through Day 29, and serious adverse events and adverse events leading to withdrawal at any time during the study. All safety data will be tabulated according to pre-exposure status and at the time points of assessment.

Exploratory Endpoints	
 • Cellular immune responses to chikungunya antigens: PBMCs will be collected on Days 1, 8, 29, 57 and 182 in order to determine the nature and stability of the cellular immune response to PXVX0317. • Humoral immune responses at other time points, to other pathogens (including EEEV and WEEV) and using other thresholds than those specified above may be performed in selected subjects. • Neutralizing antibody titers to alphaviruses will be measured at three time points (Day 1 (pre-vaccination), Day 22, and Day 182).
INVESTIGATIONAL PRODUCT	
PXVX0317, a purified CHIKV VLP vaccine, 40 mcg per 0.8 mL in Alhydrogel® adjuvant, will be administered intramuscularly (IM) on one occasion. The dose used in this study was selected based on the immunogenicity of this regimen in a previously conducted dose-finding Phase 2 trial, PXVX-CV-317-001.

CONTROL	
All study participants will receive the same Investigational Product according to the same schedule. The alphavirus vaccine naïve subjects will serve as controls for determining the effect of pre-existing alphavirus immunity on vaccine safety and immunogenicity.

STUDY POPULATION	
Up to 60 healthy adults (with replacements allowed for those who drop out prior to Day 29), including 30 prior recipients of

	investigational alphavirus vaccines, recruited from USAMRIID, and an equal number of gender and age-matched controls recruited from WRAIR.
INCLUSION CRITERIA	
 1. Age 18 to 65 years old (inclusive) 2. For women of childbearing potential, a negative pregnancy test at screening and on vaccination day, practicing highly effective contraception for at least 30 days prior to vaccination, and willing to use a highly effective method of contraception through study completion. 3. Able and willing to provide informed consent for study participation prior to screening procedures. 4. Free of obvious health problems as established by medical history and clinical examination at screening and enrollment. 5. Available to participate for the duration of the study (approximately 8 months). 6. For the cohort of prior alphavirus vaccine recipients, a documented history of prior alphavirus vaccination.
EXCLUSION CRITERIA	
 1. Acute disease or febrile illness at the time of screening or enrollment. 2. Clinically significant cardiac, respiratory, rheumatologic or other medical or psychiatric condition that, in the opinion of the Investigator, places the subject at increased risk or affects their ability to understand and comply with study procedures. 3. Abnormal screening lab test result that, in the opinion of the investigator, obscures interpretation of the safety data or suggests a clinically significant cardiac, respiratory, rheumatologic or other medical condition that places the subject at increased risk. 4. Pregnant, lactating or planning to become pregnant during the study period. 5. Laboratory evidence of infection with Hepatitis B, C or HIV. 6. History of naturally (non-laboratory) acquired chikungunya or other alphavirus infection or travel to a WHO-designated chikungunya-endemic region within 30 days prior to Day 1. 7. History of acute allergic reaction to any component of CHIKV-VLP vaccine or Alhydrogel®. 8. Current (30 days prior to Day 1) or anticipated use of systemic immunomodulatory or immunosuppressive medications.

	
 9. History of splenectomy, immunosuppressive condition, autoimmune disease, or immunodeficient condition. 10. Family history of congenital or hereditary immunodeficiency. 11. Suspected or known current alcohol or drug abuse that, in the opinion of the investigator, would interfere with the subject's ability to understand and comply with study procedures. 12. Current intravenous drug use. 13. Prior receipt of an investigational chikungunya vaccine. 14. Receipt or planned receipt of any licensed vaccine from 30 days prior to Day 1 through the Day 29 study visit. 15. Participation in another clinical trial during the study period in which an investigational product is administered. 16. For the cohort of alphavirus naïve vaccine recipients, history of prior alphavirus vaccination is exclusionary.
STUDY DESIGN	
This is a Phase 2 parallel-group, open label study in healthy adults 18-65 years of age. A total of 60 subjects are planned to be enrolled with up to 30 at each of two sites.
 
This study has a screening period of 60 days, a treatment and observation period from Day 1 to Day 29, and a follow-up period through Day 182. Subjects enrolled at USAMRIID will be matched by age (± 3 years) and gender (both birth and self-identified) with alphavirus naïve subjects enrolled at WRAIR. This matching is done to ensure that demographic characteristics are comparable between the groups, not to pair data between two specific individuals.
 
Details of visits, visit windows, and procedures are provided in the Schedule of Events (Appendix A). After signing the informed consent form, subjects will undergo screening procedures up to 60 days before the first injection. Subjects will be observed in clinic for 30 to 60 minutes after injection. Local and systemic solicited events occurring within 7 days after the injection will be recorded by the subject using a memory aid. Subjects will be specifically asked to record local injection site events (pain, redness, swelling) and systemic events (fever with oral temperature $\geq 100.4^{\circ}$ F, chills, fatigue, malaise, headache, myalgia, arthralgia, and nausea). Any other adverse events and medications used through Day 29 will also be recorded. Blood will be collected at Day 1 (before the injection) and Days 8, 22, 29, 57 and 182.

	
A final analysis of data collected throughout the study from all subjects will be performed after the last subject has completed the study and the immunogenicity and safety data have been locked.

STATISTICAL METHODS	
The primary immunogenicity analysis will compare prior alphavirus vaccine recipients to alphavirus-naïve controls on the proportion in each group who seroconvert at Day 22 – three weeks after injection – where seroconversion is defined as a 4-fold or greater rise over baseline in anti-CHIKV neutralizing antibodies as assessed by a luciferase-based assay. The statistical significance of the comparison will be assessed using a Fisher's exact test. The percentage who seroconvert in each group will be presented along with its 95% CI calculated using the Wilson method. Similar methods will be used to compare groups on the percentage of subjects who achieve a titer of at least 40, 160, or 640 at Day 22 (primary time point) and on Days 8, 57 and 182 (secondary time points).
 
GMT will be assessed using an analysis of covariance (ANCOVA) with logarithmically-transformed, anti-CHIKV neutralizing titers (\log_{10}) as the dependent variable and pre-exposure group, age, gender as fixed effects and baseline titer as the covariate in the model. The least square means and 95% CIs estimated from the model will be back-transformed and reported as the group GMT values. The geometric mean ratio (GMR) of the two groups and its 95% CI will be estimated from a model contrast.
 
Similar methods will be used to assess neutralizing and total antibody titers to other alphaviruses (VEEV, WEEV, EEEV) at other time points. Safety will be assessed primarily through the reporting of solicited and unsolicited AEs. Solicited AEs will be summarized for the 7-day period following the injection by the incidence of each type of AE, the first day of its onset, the number of days the AE was reported, and the maximum severity of the AE. Groups will be compared on the incidence of each type of solicited AE using pairwise Fisher's exact tests
 
Unsolicited AEs will be summarized by System Organ Class and Preferred Term, by severity and by potential relationship to the vaccine. Additional displays will summarize any SAEs or AEs that lead to withdrawal or death.

Displays of solicited and unsolicited AEs will present data separately for prior alphavirus vaccine recipients, alphavirus-naïve controls, and for all subjects combined.

Sample Size and Power Considerations

The sample size for this trial was based on the number of subjects in the Fort Detrick Special Immunization/Special Procedures Program who are available for screening at USAMRIID. Of the approximately 60 available subjects, up to 30 are expected to enroll in this trial along with an equal number of alphavirus naïve age- and gender-matched controls. Based on an interim analysis in Study PXVX0317-001, at least 95% of the alphavirus-naïve controls are expected to seroconvert in this trial. Assuming that the alphavirus-naïve group has a 95% seroconversion rate, a total sample size of 60 subjects has 80% power to detect a significant difference between groups if the seroconversion rate in the prior alphavirus vaccine recipients is 65% or lower. Or, in other words, power is 80% to detect a difference between groups if the seroconversion rate in the prior alphavirus recipients is 30 percentage points lower than in the alphavirus-naïve group.

Previous studies have shown impaired immune responses to chikungunya vaccines in prior recipients of live attenuated and inactivated alphavirus vaccines. The decrease in seroconversion in two of these trials was 64% and 100% respectively (see section 1.3). Therefore, this study is adequately powered to detect immune interference on the order of one-half to one-third of what has previously been described. The power of other combinations of seroconversion rate and sample size can be seen in Table 3 in section 9.1.

With respect to safety as a study endpoint, this study will have 80% power to detect a 30% difference between pre-exposure groups in the incidence of any single or aggregate solicited adverse event expected to occur in 5% of the subjects in one of the groups. With a total of 60 subjects receiving PXVX0317, there is a 95% chance that an uncommon AE – one expected to occur in 5% of vaccine recipients – will be observed at least once in the trial.

TABLE OF CONTENTS

	Page
CLINICAL STUDY PROTOCOL	1
PROTOCOL SIGNATURE SHEET	2
PROTOCOL SYNOPSIS	3
TABLE OF CONTENTS	10
1 INTRODUCTION.....	19
1.1 Background	19
1.1.1 Chikungunya Virus and Chikungunya Fever.....	19
1.1.2 Venezuelan Equine Encephalitis Virus and Vaccines	20
1.1.3 Alphavirus Immune Interference	22
1.2 Name and Description of Investigational Vaccine	22
1.2.1 Summary of Findings from Nonclinical Studies	22
1.2.2 Summary of Findings from Clinical Studies	25
1.2.2.1 VRC 311	25
1.2.2.2 VRC 704	25
1.2.2.3 PXVX-CV-317-001	26

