9 STATISTICAL ANALYSIS

9.1 Sample Size Calculation

The sample size here was chosen based on the number of subjects in the Fort Detrick Special Immunization/Special Procedures Program (USAMRIID) who are available for screening. Of the approximately 60 available, 30 are expected to enroll in this trial along with an equal number of alphavirus naïve age- and gender-matched subjects. Based on an interim analysis of this vaccine lot and regimen in Study PXVX0317-001, at least 95% of the alphavirus-naïve controls are expected to seroconvert in this trial. Assuming that the alphavirus-naïve group has a 95% seroconversion rate, a total sample size of 60 subjects affords 80% power to detect a significant difference between groups if the seroconversion rate in the prior alphavirus vaccine recipients is 65% or less. Or, in other words, power is 80% to detect a difference between groups if the seroconversion rate in the prior alphavirus recipients is 30 percentage points lower than in the alphavirus-naïve group. Compared to the previously cited studies in which decrements in the proportion of seroconversion of 64% (McClain 1998) and 100% (Harrison 1971) (DeMeio 1979) were seen, this study is adequately powered to detect immune interference on the order of one-half to one-third of what has previously been described.

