In the event that we have overestimated the willingness of this pool of eligible subjects to participate, the ability to detect differences in the proportion of seroconversion of the same order as was previously shown by McClain (36% versus 95% seroconversion), 10 subjects per group would afford 71% power to detect a significant difference. The power of other combinations of seroconversion rate and sample size can be seen in Table 3. For example, 10 subjects per group afford 81% power to detect a difference between groups if the seroconversion rate is as low as 30% in the prior alphavirus vaccine recipients, while 20 subjects per group provide 89% power to detect a difference if the seroconversion rate is 50% or lower among prior alphavirus recipients. This is certainly less than ideal in terms of designing a field study in an area endemic for other alphaviruses. The decision to conduct such a study will be dependent on many factors and the residual possibility that a lesser degree of immune interference may have gone undetected will have to be considered. If, on the other hand, immune interference on the order of that reported by DeMeio is seen in which a neutralizing antibody response is entirely abrogated, data from this study would be sufficiently compelling to avoid recruiting for field studies in areas co-endemic for other alphaviruses.

Table 3: Power of Detecting a Significant Difference between Prior Alphavirus Vaccine Recipients and Alphavirus-naïve Vaccine Recipients with a 95% Seroconversion Rate

Number of Subjects per Arm	Seroconversion Rate among Prior Alphavirus Vaccine Recipients				
	30%	40%	50%	60%	70%
10	81%	63%	43%	24%	9%
20	> 99%	97%	89%	72%	45%
30	> 99%	> 99%	98%	89%	63%

Power of each combination estimated from a Fisher's exact test comparing the seroconversion rate observed among prior alphavirus vaccine recipients to the rate observed among alphavirus-naïve vaccine recipients assuming the true rate in the latter group is 95%.

With respect to safety as a study endpoint, this study will have 80% power to detect a 30% difference between pre-exposure groups in the incidence of any single or aggregate solicited adverse event expected to occur in 5% of the subjects in one of the groups. With a total of 60 subjects receiving PXVX0317, there is a 95% chance that an uncommon AE – one expected to occur in 5% of vaccinees – will be observed at least once in the trial.

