9.6 Immunogenicity Analysis

All tests will be carried out at a 2-sided significance level of 0.05 and no adjustment for multiplicity will be applied.

Seroconversion Analysis:

The primary immunogenicity analysis will compare prior alphavirus vaccine recipients to alphavirus-naïve controls on the proportion in each group who seroconvert by anti-CHIKV neutralizing antibody at Day 22. Seroconversion is defined as a 4-fold or greater rise over baseline in anti-CHIKV neutralizing antibodies as assessed by a luciferase-based assay.

Specifically, we will test the hypotheses:

$$H_0: P_1 = P_2 \text{ vs. } H_1: P_1 \neq P_2$$

where P_1 and P_2 denote the proportion of subjects who seroconvert in the prior alphavirus vaccine recipients and the alphavirus-naïve controls, respectively.

The significance of the comparison of the pre-exposure groups will be assessed using a Fisher's exact test. The percentage who seroconvert in each group will be presented along with its 95% CI calculated using the Wilson method. A sensitivity analysis of the comparison will be performed using a logistic regression model that incorporates age, gender, and baseline titer as potential predictive factors. Fisher's test comparing seroconversion rates at other time points may also be performed. Similar analyses of the proportion who seroconvert will be conducted on Days 8, 29, 57 and 182 for anti-CHIKV neutralizing antibody and on Days 22 and 29 for total anti-CHIKV, total anti-VEEV and neutralizing anti-VEEV antibodies (secondary endpoints).

Threshold analyses:

The percentage of subjects achieving specified thresholds (e.g., ≥ 40 , 160, and 640 anti-CHIKV antibody titers), and associated Wilson 95% CIs, will also be calculated for Days 1, 8, 22, 29, 57 and 182 for neutralizing antibody and at Days 1, 22 and 29 for total anti-CHIKV, total anti-VEEV and neutralizing anti-VEEV antibodies (secondary end-points). The groups will be compared by pairwise Fisher's exact tests on the percentage achieving each threshold.

GMT analyses:

For the secondary comparisons based on GMT, the hypotheses tested will be

$$H_0: \mu_1 = \mu_2 \text{ vs. } H_1: \mu_1 \neq \mu_2$$

where μ_1 and μ_2 denote the GMT for the prior alphavirus vaccine recipients and the alphavirus-naïve controls, respectively.

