The GMTs on Days 22 and 29 will be compared for differences between the pre-exposure groups. The GMTs and Geometric Mean Ratios (GMRs) will be analyzed via linear model. The primary model is an analysis of covariance (ANCOVA), with logarithmically-transformed titers (\log_{10}) as

the dependent variable and pre-exposure group, age, gender, as fixed effects and baseline log-transformed titer as the covariate in the model. The least square means estimated from the ANCOVA and their 95% CIs will be back-transformed and reported as the group GMT values. The GMR comparing the pre-exposure groups will be calculated by back-transforming the difference estimated from a linear contrast in the model. The 95% CI for the GMR will be calculated analogously.

The GMTs and GMRs based on antibody titers measured at all other protocol-specified time points will be analyzed as described above for Day 22. The difference in persistence of the antibody response induced after first vaccination at each time point will be visually assessed.

Summaries of both seroconversion and GMT will be presented by age and gender.

Exploratory endpoints (both categorical and continuous) for the heterologous alphavirus analyses will be analyzed descriptively.

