6.2.1. Analysis Methods for Secondary Immunogenicity Endpoints

The same method used for the primary immunogenicity analysis, excluding the estimated difference, will also be used for the secondary analysis of seroresponse rate, comparing the proportion of prior alpha subjects to the proportion of naïve alpha subjects having seroresponse by anti-CHIKV neutralizing antibodies on Days 8, 29, 57 and 182 and by anti-CHIKV total antibodies and anti-VEEV total and neutralizing antibodies on Days 22 and 29.

For the secondary analysis of GMT and GMR, the GMTs and GMRs at the specified time points will be compared for differences between the two study arms (prior alpha vs. naïve alpha) for each type of antibody listed above.

The primary model used for the immunogenicity evaluable population is an analysis of variance (ANOVA), with logarithmically-transformed (\log_{10}) titers as the dependent variable and study arm, age, and gender as the predictor variables in the model. The primary model used for the mITT population is the same except that \log_{10} baseline titer will be added as a predictor if there are subjects with measurable titers in the naïve alpha group at baseline. If any baseline titer is equal to zero, then one will be added to all baseline titers prior to taking the log. The least square means estimated from the ANOVA (or ANCOVA) and their 95% CIs will be back-transformed and reported as the group GMT values. The geometric mean ratio of the prior alpha group to the naïve alpha group, and its 95% CI, will be calculated by specifying a linear contrast between the groups in the model. Since the linear contrast yields a difference between groups in log-transformed space, the difference will be exponentiated to produce a geometric mean ratio of one group to the other. The p-value associated with each model comparison will also be reported. Additionally, the median, minimum and maximum will be summarized based on the non-transformed scale.

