2. STATISTICAL CONSIDERATIONS

The Statistical Analysis Plan (SAP) called for the following secondary endpoints:

Anti-CHIKV total antibodies, determined by immunoassay, in prior alpha subjects vs. naïve alpha subjects, assessed by

- The proportion of subjects with titers of at least [REDACTED] on Days 1, 22 and 29

Anti-VEEV total antibodies, determined by immunoassay, in prior alpha subjects vs. naïve alpha subjects, assessed by

- The proportion of subjects with titers of at least [REDACTED] at Days 1, 22 and 29

It was determined post database lock, that the threshold analysis of the anti-CHIKV total and anti-VEEV total antibodies had no valuable meaning with respect to historical sero-epidemiologic protection. Therefore, the CSR team decided that these summaries should be eliminated from the final set of tables.

Also included in the original TOC for the mock tables were cumulative percentages of subjects reaching 4-fold. Because all subjects experienced 4-fold rise by the second timepoint and the groups remained at 100% throughout the study, these tables (mITT and IEP) were considered moot and not produced (they exactly mimic the by-visit summary table).

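### The between-arm difference in antibody persistence is left to visual assessment: no planned output gives a confidence interval or test for differential decline from the Day 22 peak to Day 182

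*Protocol*

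**What the plan says.** The Protocol Synopsis lists, among the secondary endpoints for CHIKV neutralizing antibody, "Geometric mean titer (GMT) and geometric mean ratio (GMR) on Days 1, 8, 22, 29, 57 and 182". Protocol 9.6 (GMT analyses) gives titers at every other protocol-specified time point the linear model described for Day 22. It then turns to durability: "The difference in persistence of the antibody response induced after first vaccination at each time point will be visually assessed".

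SAP 6.2.1 does not repeat that sentence, and SAP Section 8 does not list it as a change. The SAP says that "the GMTs and GMRs at the specified time points will be compared for differences between the two study arms". The model for log10 titer has arm, age and gender, plus baseline titer in the mITT population under a stated condition. Its outputs are a GMR, a 95% CI and a p-value at each visit.

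SAP 6.2.1 also plans fold-increase over baseline at each visit, with a between-arm t-test on the log10 scale. Titers of at least 40, 100, 160 and 640 are compared at each visit, Day 182 included, by Fisher's exact test. Figures 14.2.2.3 and 14.2.2.4 plot GMT and fold-increase over time.

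Addendum 1 drops the cumulative tables: "Because all subjects experienced 4-fold rise by the second timepoint and the groups remained at 100% throughout the study". The Day 1, 22 and 182 analyses in Addendum 2 are again done one time point at a time.

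**The concern.** The Protocol names a between-arm difference in persistence as something to assess, and its only stated method is inspection of curves. Everything formal in the plan compares the arms at one visit, or compares one visit with baseline. None of it asks whether titers fall faster in one arm between the expected peak (Day 22, Protocol 2.4.2) and Day 182.

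Protocol 1.3 asks whether earlier alphavirus exposure diminishes or enhances the response. Protocol 1.3.1 chose the regimen partly on titers maintained at Day 182, so durability matters to the programme. Without a planned contrast, a statement in the study report that antibody wanes similarly, or differently, in prior recipients would have no interval behind it. A reader would also have two p-values to set side by side, and a difference between two p-values is not a test of a difference in decline.

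**Working it through.** **Inputs from the documents.** Significance level: "All tests will be carried out at a 2-sided significance level of 0.05 and no adjustment for multiplicity will be applied" (Protocol 9.6). Sample size: "Of the approximately 60 available, 30 are expected to enroll in this trial along with an equal number of alphavirus naïve age- and gender-matched subjects" (Protocol 9.1), so 30 per arm. Expected peak: Day 22 (Protocol 2.4.2). The documents give neither the SD of log10 titer nor the correlation between Day 22 and Day 182, so both are assumed and shown as ranges.

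**1. The plan's own figure.** Protocol 9.1 states that "a total sample size of 60 subjects affords 80% power to detect a significant difference between groups" at 95% versus 65% seroconversion. Exact enumeration of Fisher's test with 30 per arm gives 78.8%, close to the stated 80%, and all 15 cells of Table 3 reproduce. These figures concern Day 22 seroconversion only. The documents give no precision or power figure for any GMR or for persistence.

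**2. What each planned analysis compares.**
- Per-visit GMR with CI and p-value: level at one visit.
- Fold-increase t-test: one visit against baseline, not against the peak.
- Threshold and seroresponse tests: proportions at one visit.
- Figures over time: trajectory, with no planned contrast.

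**3. A point estimate can be derived.** With the same subjects and covariates at both visits,

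log10(GMR182) − log10(GMR22) = arm effect in a model of (log10 titer Day 182 − log10 titer Day 22).

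In a simulated complete data set of 60 subjects, the two per-visit GMRs were 0.8591 (Day 22) and 0.5634 (Day 182). Their quotient, 0.5634/0.8591 = 0.656, equals the arm effect from the change model, 0.656. The identity fails if some subjects lack a Day 182 titer. That can happen, because the IEP requires only baseline and Day 22 samples (SAP 3.1.5) and no titers are imputed (SAP 3.2).

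**4. Its confidence interval cannot be derived.** The variance of the difference is V22 + V182 − 2·Cov, and the covariance is not among the planned outputs. With a common SD and correlation ρ:

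half-width (log10) = t(58) × SD × √(2(1−ρ)) × √(2/30), with t(58) = 2.00.

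At SD 0.4 the interval is the estimate multiplied or divided by 1.96 if the two GMRs are treated as independent (ρ = 0), by 1.61 at ρ = 0.5, and by 1.24 at ρ = 0.9. The reader cannot tell which applies.

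**5. What a formal contrast could detect.** At SD 0.5 and ρ = 0.7:
- SD of change = 0.5 × √0.6 = 0.387
- SE = 0.387 × √(2/30) = 0.100
- significant at 10^(2.00 × 0.100) ≈ 1.59-fold
- power for a 2-fold difference (log10 2 = 0.301, noncentral t, 58 df) = 84%

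Power for a 2-fold difference in decline, 30 per arm, same formula:

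| log10 SD | ρ = 0.5 | ρ = 0.7 | ρ = 0.85 |
|---|---|---|---|
| 0.4 | 82% | 96% | 99.9% |
| 0.5 | 63% | 84% | 99% |
| 0.6 | 48% | 69% | 94% |

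With 25 per arm at Day 182, the case SD 0.5, ρ = 0.7 gives 77%. The calculation ignores the small effect of adjusting for age and gender.

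**The case against.** The strongest reply is that durability is not left wholly to the eye. Day 182 has a GMR with CI and p-value, a fold-increase t-test, and Fisher's tests at four thresholds. One of these is 640, which Protocol 1.3.1 uses to describe maintenance of response (44% at Day 182 in the earlier study). In a 60-subject phase 2 trial that already runs many unadjusted tests, inspecting curves beside those comparisons is defensible. Rate of waning is not a listed objective or endpoint in either document. All of that stands, and it limits the weight of the point.

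A reader might infer more than the documents support:
- **That persistence is compared only visually.** The level at Day 182 is tested formally. Only the change from peak is not.
- **That no estimate is possible.** In complete data the quotient of two planned GMRs is a valid estimate.
- **That differential waning is why blood is drawn at Day 182.** Neither document says so.
- **That real differences would usually be missed because persistence would be judged by overlapping intervals or by p-values that disagree.** The plan states no such rule, so error rates computed for those rules do not describe it.
- **That ceiling seroresponse was a visible design flaw.** The 100% result comes from an addendum recording decisions made after database lock. It shows that seroresponse at Days 57 and 182 tells little about persistence, but it was known only in hindsight.

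What the reply does not answer is that none of these comparisons yields an interval or test for the difference in decline that Protocol 9.6 says will be assessed.

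**Conclusion.** The point holds in a limited form. The Protocol names a between-arm difference in persistence, gives it visual assessment alone, and no later document supplies a within-subject comparison of Day 182 with Day 22. The missing items are the confidence interval and the test. A point estimate is recoverable by hand when both visits use the same subjects and covariates.

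How much a formal contrast would add depends on two quantities that the documents do not give. Over log10 SD 0.4 to 0.6 and correlation 0.5 to 0.85 with 30 per arm, power for a 2-fold difference in decline runs from about 48% to 99.9%. It would therefore be informative in much of that range and weak at its unfavourable end, where the interval would at least show how little is known. This is a cheap improvement to a secondary description and does not touch the primary analysis.

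**What to change.** In Protocol 9.6, replace the visual assessment with a stated contrast, and add to SAP 6.2.1 for CHIKV NT80 a supportive secondary analysis along these lines:

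> The between-arm difference in persistence will be estimated as the ratio (prior alpha to naïve alpha) of geometric mean Day 182/Day 22 titer ratios, with 95% CI, from a linear model of the within-subject log10 change with study arm, age and gender.

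An arm-by-visit contrast in a repeated-measures model of log10 titer is an alternative. It matches the change model in complete data if the age and gender effects may differ by visit, and it also uses subjects whose Day 182 sample is missing. State which of the two below-LOD conventions in SAP 3.3 applies. Keep the per-visit GMRs and the figures. If the analysis is added after database lock, label it post hoc.

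The cost is one SAP paragraph and one table from data already collected. The downside is one more secondary estimate without multiplicity adjustment.
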